The combined use of these lasers represents a novel approach to addressing diverse skin care goals. To our knowledge, this is the first study to investigate the combined effects of these three modalities on skin rejuvenation and overall skin health in a single setting.

Device	Characteristics	Wavelength	Target	Previous Studies
BBL Broad based light (BBL HERO)	IPL Nonablative		Freckles Age Spots Cherry Angiomas Rosacea Dull complexion Acne Skin Laxity Unwanted hair	Berlin et al 2007 Siperstein et al 2021 Handler et al 2017
MOXI	Fractionated thulium Nonablative (1927 nm laser)		Pigmentation Sun damage (UV spots) Signs of aging (brown spots)	Vingan et al . 2023 Li et al 2023
HALO	Dual fractionated hybrid laser Non-ablative (1470 nm) & Ablative (2940 nm)		Fine lines & Wrinkles Sun damage & dyschromia Scar revision Pigmented lesions Enlarged pores	Kislevitz et al 2020 Waibel et al 2018

Purpose

This single-site clinical trial is being conducted over the course of 4 to 6 months. Healthy subjects will receive 1-2 treatments combining BBL/MOXI/HALO during this trial and be followed up 1 month and 3 months after their final treatment to assess noted changes.

The primary objective of the study is to assess the efficacy of this BBL/MOXI/HALO combination treatment.

Project Summary

Clinical Study

This is a single-site, non-randomized, non-controlled study at UT Southwestern Medical Center at Dallas in the Department of Plastic Surgery. The study is designed to follow up to 15 consenting subjects who may receive up to 2 BBL/MOXI/HALO treatments under an IRB approved protocol. The BBL/MOXI/Halo treatments are all within the Joule System and is used as separate or combination treatments as part of standard of care within the clinic.

The Principal Investigator (PI) has been selected based on expertise, qualifications, previous clinical research and interest in this field of research. Subjects will be identified and recruited from the clinic of plastic surgery at UT Southwestern Medical Center.

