Subjects will be consented by a member of the research team and subjects will be numbered in the order that consent is obtained, and all assessments and documents will contain the assigned ID for the duration of the study. Subjects will receive 1-2 BBL/MOXI/HALO treatments. All 2nd treatments will be scheduled 4-8 weeks after the initial treatment to ensure the skin has enough time to recover. Overall assessments will be collected before the first treatment and at subsequent follow-up visits at 1 Month and 3 Months post final treatment. Identifiable full-face standard and close-up photography will be obtained and used to evaluate any changes. Subjects will also have photos obtained with the VISIA-CR Imaging System (Canfield Scientific, Parsippany, NJ). Quantitative analysis will be completed on the VISIA imaging system and be used to compare the effects of the treatments. Any improvements will be evaluated to pre-treatment assessments.

Primary Endpoints

Assessment of changes by VISIA Imaging System of photos obtained pre-treatment, 1 Month and 3 Months post-treatment.

- Calculate percent change from baseline in numeric analysis via the VISIA Imaging System
 - VISIA- CR Imaging system will be utilized to capture qualitative and quantitative data including, but not limited to: spots, wrinkles, texture, pores, UV spots, brown spots, red areas and porphyrins.
 - Clinician assessment of improvement using the Global Aesthetic Improvement Scale.

Secondary Endpoint

Monitor incidence, severity and relatedness of adverse events throughout the study.

Study Device Information

	Proprietary Information	Device Description	Regulatory Information
Device Name:	Sciton BBL HERO	Aesthetic device utilizing broadband light to improve the appearance of aging, reduces rosacea, acne, melasma and sun spots	
JOULE Multi-Platform System	Sciton MOXI	Aesthetic laser device that utilizes a fractionated laser to treat uneven pigmentation and heal photodamage skin	Class II 510(K) Number: N/A Regulation number: 878.4810
	Sciton HALO	Aesthetic laser device that utilizes a hybrid fractionated laser to treat fine lines & wrinkles and reduce the appearance of enlarged pores, sun damage and dyschromia	

Study Population & Enrollment

Enrollment

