- <6 months of non-ablative, rejuvenative laser or light treatment
- <3 months of chemical peels or dermabrasion

12. Use of the following prescription medications:

- <6 weeks of Accutane or other systemic retinoids on the treatment area
- <4 weeks of topical retinoids
- <4 months of prescription strength lightening medications (e.g., hydroquinone, tretinoin, AHA, BHA, poly-hydroxy acids, 4-hydroxyanisole alone or in combination with tretinoin)
- <2 weeks of anti-wrinkle or skin lightening or topical systemic medication known to affect skin aging or dyschromia (e.g., alpha/beta/polyhydroxy acids, Vitamin C, soy, Q-10; hydroquinone, etc.,), TEGO, Cosmo C250, gigawhite, lemon juice extract (topically), or embilica extract
- Antiplatelet agents/anticoagulant (Coumadin, Heparin, Plavix, chronic NSAID use)
- Psychiatric drugs that would impair the subject from understanding protocol requirements or understanding and signing the ICF.

13. Individuals who are pregnant or planning to become pregnant during the course of the study

14. Immunocompromised individuals or those currently using immunosuppressive medications and/or radiation

15. Individuals with uncontrolled disease such as asthma, diabetes, hyperthyroidism, medically significant hypertension, or hypothyroidism.

16. Individuals with any planned surgeries, overnight hospitalization, and/or invasive medical procedures planned during the course of the study.

17. Individuals who, in the Investigator's opinion, have a history of poor cooperation, unreliability or noncompliance with medical treatment.

18. Individuals who are unable to understand instructions or give informed consent

19. Individuals who have physical or psychological conditions which, in the opinion of the Investigator, makes them unable to complete the study per protocol.

Study Timeline

Outline of Visits

[figure not shown]
Single Treatment Arm

Study Procedures		Visit 1 Screening (Day -45 to 0)	Visit 2 Treatment #1 (Day 0)	Visit 3 Follow-Up #1 PI Assessment Tx1 1M (Day 30)	Visit 4 Follow-Up #2 Tx1 3M (Day 90)
Demographic & Eligibility	Informed Consent ; Eligibility Criteria Medical History & Demographics	X			
Safety Assessments	Adverse Events; Concomitant Medications		X	X*	X
Study Intervention	BBL /MOXI/ Halo		X		
Assessments	Standard Photography; VISIA Imaging/Analysis	X		X	X
Evaluations	Global Aesthetic Improvement Scale				X

Dual Treatment Arm

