After the procedure, subjects will be provided appropriate post-treatment care instructions as deemed appropriate by the Investigator or study staff. Subjects will be instructed that blistering, bleeding, oozing, strong pain, swelling persisting for more than 72 hours, or signs of infection (e.g., pus, drainage, fever) are cause for immediate concern and they should contact the investigator and/or his designee, to be evaluated. Expected downtime after BBL/MOXI/HALO is expected to be 7-10 days.

The treatment visit(s) is expected to take approximately 1 hour.

*A subset of subjects will return for a second treatment 45-60 days after the initial treatment. The PI and/or Sponsor will make a determination if a second treatment would be beneficial to the subject. All follow up visits will be scheduled accordingly.

PI Assessment: Visit 3 (1-month follow-up from initial treatment)

The physician will assess the patient at their 1-month follow-up after the initial treatment. The treating physician will determine if a single treatment is sufficient for achieving aesthetic goals or a second treatment is indicated based on the patient's presentation. Candidacy for a second treatment may involve assessment of the following factors:

- Stage of healing
- Absence of complications and adverse events
- Treatment tolerance by patient
- Patient interest and consent
- Review of VISIA data and Photography

Follow Up Visits (1M & 3M post final treatment): Visit 3 & 4 (Single tx) or Visit 5 & 6 (Double tx)

At a minimum, all subjects will return for follow-up visits at 1 month (\pm 7 days) and 3 months (\pm 7 days) after the final treatment.

The following activities will be performed on all study subjects during the follow-up visits:

1. The physician or study staff will ask subjects if they have experienced any changes in their health since the previous visit. Changes will be recorded accordingly. If an adverse event (AE) is reported then the Investigator will be informed, and an AE form will be completed.
2. Subjects will acclimate to ambient temperature and humidity conditions for 15 minutes prior to any procedures being done.
3. The physician or study staff will perform an examination of the skin in the treatment area
4. Obtain post-treatment close-range and standard photography as described in section entitled, "Assessments", for research purposes.

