5. Obtain post-treatment photographs and measurements using the Vectra H2 3D Imaging System and VISIA Imaging System as described in section entitled, "Assessments", for research purposes.

These visits will take about 30 minutes.

Assessments

Photography Procedures

NIKON D7200

Standard and close-range of the face will be utilized for evaluation of pigmentation. These photographs will be taken utilizing the Nikon D7200 at Baseline (Screening Visit), 1-month post-treatment and 3-months post-treatment.

VISIA CR Imaging System

Subjects will be instructed to adopt neutral, non-smiling expressions for each photograph. Images will be taken of each applicable subject with diffuse pigmentation of the face using the Vectra H2 3D Imaging System at Baseline, 1-month post-treatment and 3-months post-treatment. Each subject will have a total of 3 photos taken (right side, left side and center view).

Potential Risks

Risks of Anesthetic

Allergic Reaction (Rare)

There is a possibility of an allergic or toxic reaction to anesthesia used to numb the areas. Subjects will be questioned with regard to any history of allergies and carefully monitored for signs of allergic reaction.

Risks of Treatments

BBL: Broad Band Light

Erythema: (Occasionally < 3%)

May develop within the irradiated areas but are usually temporary and fade within 24-72 hours. There is a 90% chance of transient edema and 99% chance of erythema to occur after treatment.

Swelling and/or itching: (Occasional <3%)

May occur in the area of treatment and may last up to several hours. The pattern of the treatment may be visible on the skin, but this usually fades with healing. Itching and hive-like appearance may also occur.

Bruising: (Rare < 1%)

A mild bruising may occur at the treatment area as a result of laser exposure. This is usually transient and resolves in a few hours to few days.

Skin roughness and/or peeling (Occasional <3%)

Patients can expect their treated skin to feel rough like sandpaper for a few days while the skin heals. This is transient and should resolve in a few days.

Lasers: MOXI (Non-ablative Laser Facial Resurfacing & HALO (Fractionated Laser)

Blistering, burning, scaling and infection: Rare < 1%)

A crust, blister or superficial wound can occur at the treatment area. The risk of infection will be minimized by proper wound care.

Bruising: (Rare < 1%)

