A mild bruising may occur at the treatment area as a result of laser exposure. This is usually transient and resolves in a few hours to few days.

Transient edema and/or erythema: (Occasionally < 3%)

May develop within the irradiated areas but are usually temporary and fade within 24-72 hours. There is a 90% chance of transient edema and 99% chance of erythema to occur after treatment.

Pigmentary changes: (Rare < 1%)

Laser exposure can cause pigmentary changes such as hyper- (3% chance) and hypo-pigmentation (<.5% chance). Although this is usually temporary, it may be permanent on rare occasions. Sun avoidance and/or the use of a total sun block (SPF 30 or higher) will help minimize the intensity and duration of any pigmentary changes.

Skin roughness and/or peeling (Occasional <3%)

Patients can expect their treated skin to feel rough like sandpaper for a few days while the skin heals. This is transient and should resolve in a few days.

Eye injury: (Rare < 1%)

There is a risk of eye injury associated with the use of this device. This risk will be minimized by wearing protective eyewear designated for use with this device. All subjects and other personnel must use proper protective eyewear during the use of this device.

Scarring: (Rare < 1%)

As with any form of laser exposure, there is a small risk of scarring. However, this is minimized by proper technique and wound care.

Risks of Photography:

The subject may be uncomfortable with sitting still for an extended period of time or from turning his/her body in various positions. Subjects may be sensitive to bright and repeating flashes from the camera, which can sometimes cause headaches, eye irritation, discomfort, aftereffects such as seeing spots, and in rare cases, could stimulate a migraine headache or epileptic seizure.

Photographs include a risk of identification, as these will be full face photos. Privacy will be protected to the greatest extent possible. Photos will only be identified by unique subject identification number that contains no personal

identifying information. All photos will be stored on a password secure drive, with only access by research personnel. For research purposes, photos may be used in scientific publications.

Adverse Events

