At each visit, a member of the research team will question the subject about adverse events using an open-ended question. If a potential adverse event is reported by the subject or identified during examination, directed questioning and examination will be performed when appropriate. At this time, the following will be performed:

1. Obtain a complete history of the event in question as well as conduct an examination of the subject and determine if the reported event qualifies as an Adverse Event (AE). If the event is determined to be an AE, an AE case report form and Event Follow-up (EF) visit case report form must be completed. One AE case report form should be used to track the history of an individual AE throughout the period of the study.
2. Collect an updated medical and surgical history along with recording of concomitant medications or treatments.
3. Take photographs of the subject with attention to the area in question.
4. Render treatment for the event, if any, as determined by the medical judgement of the Investigator.

Photographs will be taken to document any AEs if possible.

For the duration of the study, medical assistance will be provided to the subject for study-related problems at no expense, if in the opinion of the Investigator, the reaction was caused by BBL/MOXI/HALO treatments. Should a subject choose to seek their own medical treatment, no reimbursement will be offered.

When an AE persists at the end of the study, the Investigator will ensure a follow-up of the subject until the Investigator believes that the event is satisfactorily resolved.

Subject Safety & Data Monitoring

Research Standards and Good Clinical Practice

The conduct of this study will follow all applicable guidelines for the protection of human subjects for research as outlined in 21 CFR 50, in accordance with the accepted standards for Good Clinical Practice (GCP), International Conference on Harmonization (ICH), and the standard practices of UT Southwestern.

Data Monitoring

For this protocol, which involves the use of a non-significant risk device, the Investigator will monitor accrual, subject experience, attrition, patterns of adverse events and/or unexpected adverse events, any protocol deviations, or violations any changes in the risk/benefit analysis.

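### For about 30 days after each treatment, adverse events are captured only if the subject makes contact, so mild and moderate short-lived reactions are likely to be under-recorded or graded from recall

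*Combined protocol and SAP*

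**What the plan says.** - **Endpoint.** The Secondary Endpoint section has one item: "Monitor incidence, severity and relatedness of adverse events throughout the study".
- **Size.** The Project Summary plans for "up to 15 consenting subjects who may receive up to 2 BBL/MOXI/HALO treatments".
- **Schedule.** Under Study Timeline, the Single Treatment Arm table goes from treatment on Day 0 to Visit 3 on Day 30. The Dual Treatment Arm table has the same first interval, then goes from the second treatment on Day 45 to Visit 5 on Day 75. Nothing is scheduled inside either interval. Under Follow Up Visits, "At a minimum, all subjects will return for follow-up visits at 1 month" carries a window of 7 days either way, counted from the final treatment.
- **How events are asked about.** The Adverse Events section says "At each visit, a member of the research team will question the subject about adverse events using an open-ended question". Directed questions follow only when an event has been reported or found on examination.
- **How long reactions last.** Under Potential Risks, of redness and swelling: "May develop within the irradiated areas but are usually temporary and fade within 24-72 hours". Itching is put at hours, bruising at hours to days, roughness and peeling at days. The treatment section adds: "Expected downtime after BBL/MOXI/HALO is expected to be 7-10 days".
- **Between visits.** The Data Monitoring text asks subjects to get in touch about adverse events that arise between visits, and allows an extra visit for examination and photographs. The treatment section lists warning signs that should prompt a call: blisters, bleeding or weeping skin, marked pain, swelling lasting beyond 72 hours, and signs of infection.

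**The concern.** The reactions that the protocol itself expects begin and end inside an interval with no planned observation. Incidence and severity then depend on a subject choosing to call about a reaction that they were told to expect, or on recalling it weeks later in answer to a general question. Any resulting loss lowers the recorded count, which favours the treatment.

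Two things are at stake. First, the protocol describes itself as the first study of the three modalities together in one setting, so short-term tolerability is among the main things that it can add. Second, whether a subject is a candidate for a second treatment is judged at Visit 3 partly on tolerance and on the absence of adverse events, and that judgement draws on the same month-old information.

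**Working it through.** The documents give no adverse-event rate calculation or precision statement to reproduce. The check is date arithmetic on the schedule, followed by an illustration using the protocol's own risk percentages.

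**1. Length of the unobserved interval**
- After treatment 1: 30 − 0 = 30 days.
- After treatment 2: 75 − 45 = 30 days.
- The 7-day window puts the 1-month visit at day 23 to 37 after the final treatment. For dual-treatment subjects, Visit 3 is simply given as Day 30.

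**2. Delay from the reaction to the first scheduled question**

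| Visit, days after treatment | From 72 hours (day 3) | From end of downtime, day 7 | From end of downtime, day 10 |
|---|---|---|---|
| 23 | 20 | 16 | 13 |
| 30 | 27 | 23 | 20 |
| 37 | 34 | 30 | 27 |

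The delay is nominally 27 days from the 72-hour point (range 20-34) and 20-23 days from the end of downtime (range 13-30).

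**3. Does the treatment-day entry fill the gap?** The schedule marks adverse events at the treatment visits. The text for those visits asks about health changes since the visit before, and it stands ahead of the pre-treatment steps. As written it looks backward. No post-procedure symptom assessment is listed.

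**4. Illustration of what could be lost.** The risk section gives two incompatible frequencies for redness and swelling: a label of under 3%, and "There is a 90% chance of transient edema and 99% chance of erythema to occur after treatment". These must be reconciled, so both are carried through. The share captured, *r*, is an assumption, because the documents give none.

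At the high figures, expected subjects recorded per treatment = 15 × p × r. At the label figure, taken at its upper limit of 3%, the chance of recording at least one case = 1 − (1 − 0.03r)^15.

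| r (assumed) | Erythema, p = 0.99 | Edema, p = 0.90 | Chance of at least one, p = 0.03 |
|---|---|---|---|
| 1.00 | 14.85 | 13.50 | 36.7% |
| 0.80 | 11.88 | 10.80 | 30.5% |
| 0.50 | 7.43 | 6.75 | 20.3% |
| 0.25 | 3.71 | 3.38 | 10.7% |

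The table shows direction and sensitivity only. Nothing in the documents says which row applies.

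**The case against.** A reader of the two schedule tables might infer that no adverse-event data at all are collected between a treatment and the 1-month visit, and that events will certainly be under-counted. The documents do not support either statement.

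- The Data Monitoring text asks for contact about between-visit adverse events without a severity threshold, and provides for unscheduled evaluation with photographs. The treatment section adds a named list of warning signs. Collection is passive, not absent, and the more worrying events have a real-time route.
- Follow-up visits involve more than one question. They include an enquiry about health changes since the last visit and a skin examination, so pigment change or scarring that persists can be found without recall.
- The protocol does not say whether expected transient reactions count as adverse events. If they do not, part of the apparent loss is not a loss to the endpoint.
- There is no comparator and no test or decision rule for adverse events, so no inferential safety claim is at risk. The protocol also says the devices are already used in combination in the clinic.

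All of this stands, and it limits the point. It does not remove it. The warning-sign list leaves out bruising, itching, peeling and swelling that settles within 72 hours, and subjects are told to expect downtime. By Day 30 a reaction of that length would usually leave nothing to examine. A descriptive endpoint of incidence and severity still needs the mild and moderate events.

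**Conclusion.** The concern holds in a limited form. For about 30 days after each treatment, ascertainment is subject-initiated only, and no scheduled contact, diary or checklist covers the 24-72 hour reaction period or the 7-10 day downtime. Mild and moderate transient events are therefore likely to be under-recorded, or graded from recall 13-30 days after downtime has ended, for the only secondary endpoint.

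The size of the loss cannot be derived from the documents. It depends on how many subjects call, how well they recall, and whether expected transient reactions are counted as adverse events. The direction rests on one assumption: that unprompted reporting and late recall miss events more often than they add them. The conclusion does not extend to the listed warning signs, or to lasting changes that are visible on examination. This is a cheap improvement that should be made. It is not a flaw that invalidates the study.

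**What to change.** At each treatment visit, give the subject a one-page diary for the first 10 days. List the reactions named under Potential Risks, each with start day, end day and severity. Collect it at the next visit and name it, together with the open-ended question, as the source for the safety endpoint.

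State in the Adverse Events section how expected transient reactions are classified, and report them separately from other adverse events. Otherwise near-universal redness would make the overall incidence hard to interpret. Reconcile the under-3% labels with the 90% and 99% figures in the same entries.

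**Cost.** One form for at most 15 subjects and 15 × 2 = 30 treatments, a few minutes of existing coordinator time, IRB review of a subject-facing document, minor subject burden, and probably a slightly higher, less favourable recorded event rate. The diary is data capture only: no visit is added and no care instruction changes.

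### The risk section gives incompatible frequencies for the same reactions: erythema below 3% and 99%, edema below 3% and 90%, pigmentary change below 1% with hyperpigmentation alone at 3%

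*Combined protocol and SAP*

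**What the plan says.** The frequencies are in Potential Risks, under Risks of Treatments, which has one list for BBL and one for MOXI and HALO together.

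- **BBL, erythema.** The heading is "Erythema: (Occasionally < 3" per cent. The text beneath says: "There is a 90% chance of transient edema and 99% chance of erythema to occur after treatment".
- **BBL, swelling.** A separate item is headed "Swelling and/or itching: (Occasional <3" per cent.
- **MOXI/HALO, edema and erythema.** The heading is "Transient edema and/or erythema: (Occasionally < 3" per cent. The same 90%/99% sentence follows, word for word.
- **MOXI/HALO, pigment.** The heading is "Pigmentary changes: (Rare < 1" per cent. The text reads: "Laser exposure can cause pigmentary changes such as hyper- (3% chance) and hypo-pigmentation (<.5% chance").
- **Both lists, roughness and peeling.** The heading is below 3%, but the text tells patients to anticipate rough skin for a few days.

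Three other places bear on how these figures matter. The Secondary Endpoint is to "Monitor incidence, severity and relatedness of adverse events throughout the study". Under Data Monitoring the investigator follows "patterns of adverse events and/or unexpected adverse events" and any change in the balance of risk and benefit. The Informed Consent Form section says that the form will explain the study's risks.

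**The concern.** A reaction cannot be both uncommon and nearly certain when it is counted in the same way. Nor can a class of events be rarer than one of its members, as the pigment item implies.

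Nothing in the documents says that heading and text count different things. The natural rescue is that headings count persistent reactions and the text counts transient ones. It fails for MOXI/HALO edema and erythema, because that heading itself specifies transient reactions.

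Adverse events are the trial's only secondary endpoint, and these are the only risk frequencies that the protocol states. An investigator who wants to know whether a reaction is appearing more often than it should finds two answers. So does whoever drafts or checks the risk wording in the consent form. The pigment item matters most for disclosure: the protocol says that such changes may, rarely, be permanent, and pigmentation is one of the conditions being treated.

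**Working it through.** The plan derives no figure from these rates, so there is nothing to reproduce. The check is whether heading and text can both hold.

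**Inputs**, all from Potential Risks: headings below 3% (erythema; edema or swelling) and below 1% (pigmentary change); text 99% (erythema), 90% (edema), 3% (hyperpigmentation) and below 0.5% (hypopigmentation).

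**Step 1: what each heading bounds.** Two headings are of the and/or kind. The frequency of either reaction is at least that of each one alone, so a bound of 3% on the pair also bounds each member at 3%. Likewise, a bound of 1% on all pigmentary change bounds hyperpigmentation at 1%. For BBL edema I take swelling and edema to be the same reaction.

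**Step 2: ratio of text to heading bound.**

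| Reaction | Heading | Text | Ratio | Gap (percentage points) |
|---|---|---|---|---|
| Erythema, both lists | <3% | 99% | 99/3 = 33 | 99 − 3 = 96 |
| Edema, both lists | <3% | 90% | 90/3 = 30 | 90 − 3 = 87 |
| Pigmentary change, MOXI/HALO | <1% | 3% (hyperpigmentation alone) | 3/1 = 3 | 3 − 1 = 2 |

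Each heading is a strict upper bound, so every ratio and gap is a minimum: more than 33-fold, 30-fold and 3-fold. If hyper- and hypopigmentation never occur together, the text total is below 3 + 0.5 = 3.5%, against the same 1% bound. Hypopigmentation taken alone, below 0.5%, fits its heading.

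**Step 3: could different denominators explain it?** Suppose each heading applies per device and per session, while the text applies per subject over the whole course. The chance of at least one event is at most the sum of the separate chances, whatever their dependence.

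- Erythema and edema: 3 devices × 2 treatments × 3% = below 18%. The text figures are still at least 99/18 = 5.5 and 90/18 = 5 times larger. Even this most generous reading does not close the gap.
- Pigmentary change: 2 lasers × 2 treatments × 1% = below 4%, which could accommodate 3%. This pair could be reconciled, but only on a reading that the documents nowhere state.

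**Step 4: roughness and peeling.** The text gives no number, so no ratio can be formed. The conflict is one of wording: a reaction headed below 3% is described as what patients in general will experience.

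**The case against.** The strongest case on the other side is that nothing planned depends on these percentages. The Secondary Endpoint is descriptive, Data Monitoring has no numeric trigger, and the Statistical Analysis section does not mention adverse events. All the reactions are listed risks under either figure, so none becomes an unexpected type of event. A reader of the protocol also sees the 90% and 99% directly beneath the low heading. All of this stands, and it confines the point to internal consistency.

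Stronger readings are tempting, but the documents do not support them.

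- **That the safety endpoint rests on wrong expected rates.** The plan sets no expected rate for that endpoint.
- **That expected case counts in up to 15 subjects can be computed and compared with what is observed.** The documents do not say whether a percentage is per subject or per session, or whether the MOXI/HALO figures are for each laser or for both. Erythema and edema are said to fade within 24 to 72 hours, the next scheduled visit after the first treatment is Day 30, and questioning is open-ended. Recorded incidence may therefore estimate neither figure.
- **That subjects are being misinformed.** The consent text is not available, so this can be checked but not asserted.
- **That the higher figures are the true ones.** The documents give no source for either member of any pair.

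What the objection does not remove is the contradiction itself, or the fact that the protocol offers no other frequencies.

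**Conclusion.** The point holds as an internal inconsistency. Heading and text differ by more than 33-fold for erythema, more than 30-fold for edema and more than 3-fold for pigmentary change, with a verbal conflict for roughness and peeling. Read on the same basis, at least one figure in each numerical pair is wrong, and which one cannot be told from the documents.

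The conclusion rests on two assumptions: that a heading and the text beneath it count the same thing, and that swelling and edema are the same reaction in the BBL list. The erythema and edema conflicts survive any choice between per-device, per-session and per-subject counting. The pigment conflict needs the first assumption.

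No planned analysis, sample size or stopping rule is affected. What is affected is the reference that the investigator has for judging adverse-event patterns and changes in risk and benefit, and the figures that the consent form's risk information should match.

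**What to change.** Go back to the source data and reconcile each heading with the text beneath it, including roughness and peeling. State one frequency per reaction and modality, and say what it counts: per subject or per session, transient or persistent, and for MOXI and HALO whether it applies to each laser or to both. Then check that the consent form carries the same figures and correct it if it does not.

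No change to design, endpoints or analysis is needed, and the plan does not call for these figures to serve as formal benchmarks in the adverse-event tables. The cost is protocol wording, and consent wording where it differs. Some stated risks may look less favourable afterwards.
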